#### C.5. Recruitment and Retention

#### **C.5.1 Local Recruitment Methods**

Will subjects be recruited at the Tufts site for this study? ■ Yes
If Yes, describe the following attributes of the recruitment plan for the Tufts site(s)¹:

- 1. When, where, and how potential subjects will be recruited:
  - a. Source of subjects: Boston and the surrounding areas will serve as the source of subjects. The HNRCA Metabolic Research unit (MRU) maintains a computerized database of participant information through Protocol Manager (volunteer database centralized under the Volunteer Services Department [IRB approved protocol # 6701] and contains the names of approximately 40,000 individuals) and nCoup Volunteer (secure SaaS participant database hosted on Amazon Web Services). In addition to this database, to

Tufts Health Sciences IRB Protocol Template

<sup>1 If Tufts IRB is requested to be the Single IRB of Record for external sites (as per section K.3 Multi-Site Research), these external sites are included in "Tufts site(s)"

- identify potential participants recruitment flyers will be posted in and around the HNRCA, Tufts Medical Center/Tufts University of Health Sciences campus, and surrounding area. Social media sites such as the HNRCA website and Facebook page, will also be used.
- b. *Methods that will be used to identify potential subjects*: The HNRCA Protocol Manager and nCoup Volunteer database will be used to identify a pool of potentially eligible participants based on the protocol's inclusion/exclusion criteria and targeted mailings will be sent with information about the study. In addition to this database, to identify potential participants, recruitment flyers will be posted in and around Tufts University/HNRCA, and social media sites such as the HNRCA website and Facebook page will include a description of the study and links to forms that potential study participants can express interest in participating in this study.
- 2. If potential subjects will be approached, specify where the recruitment discussion will take place to ensure subjects' privacy (e.g. a private clinic room): Recruitment discussions will take place via a telephone call between the study staff and potential participant. There is a designated area in the HNRCA to make recruitment phone calls.
- 3. If potential subjects will be **recruited by telephone**, describe how many times the research team will attempt to call / leave a voice message: If the subject cannot be reached, a voice message will be left with information about returning the call. Three attempts will be made to call a potential subject. If no response is received, any further communication attempts regarding the study will cease.
  - a.  $\boxtimes$  Check to confirm that a script for **both** the telephone conversation and the voice message is included with the submission.
- 4. When subjects respond to recruitment material, describe the information that will be provided to them about the study and the information that will be collected from subjects (e.g. name, telephone number, etc.). Describe also, how many times you will attempt to respond to call the subject back / leave a voice message: Upon the subject's response to recruitment material (targeted mailer, social media post or flyer), they will be informed of the general purpose of the study and procedures that will take place, in addition to the time commitment for the overall study as well as each in person study visit. A research team member will also administer a brief telephone prescreening questionnaire to determine eligibility. At this time, the following will be collected; name, telephone number, email address, and mailing address for future correspondence, height, weight, age, sex, gender, menopausal status, medication and supplement use, health history and if following a dietary pattern that excludes meat. The answers to the prescreening questions related to drug and alcohol abuse will be stored in REDCAP under a separate section that has no identifiers and cannot be linked back to the participants demographic information. They will also be queried as to whether they have adequate freezer/refrigerator space to store the study entrées.
  - ☑ Check to confirm that a script for **both** the telephone conversation and the voice message is included with the submission.
- 4. Will potential subjects be recruited at institutions that are not owned and operated by Tufts Medical Center, Tufts University, MelroseWakefield Healthcare, or Lowell General: ⊠ №
- 5. If print and media advertisements will be used, specify when, where, how long and frequency of the advertisements that will be published/aired: Recruitment material will be used for the duration of the study recruitment period. Advertisements will be published on the HNRCA website, as well as other social media sites. It is anticipated recruitment will occur over a 12

month period, or until 30 participants (15 females and 15 males) have completed each of the two diet phases.

- a. \(\simega\) Check to confirm that any necessary permission will be obtained for posting/airing these (for example, permission to post a flyer on a bulletin board).
- 6. If recruitment material is being mailed or otherwise distributed, submit the proposed material and describe where/how the distribution list will be obtained: The list of potential subjects who will receive a targeted mailer will be identified via the HNRCA Protocol Manager or nCoup Volunteer database (IRB approved protocol # 6701).
- 7. Describe how the recruitment methods described will be effective in attracting the targeted subject population. Address both planned recruitment activities as well as any proposed engagement strategies for retention: Prior experience suggests that use of the HNRCA's database as well as the targeted nature of the mailings to a volunteer pool who meet the study inclusion criteria will be an effective manner to recruit subjects. Likewise, experience indicates that posting recruitment flyers in and around the Tufts Medical Center/Tufts University of Health Sciences campus and surrounding area, and social media sites such as the HNRCA website and Facebook page, are effective recruitment approaches.

## **C.5.2 Study-Wide Recruitment Methods**

Is this is a multicenter study where subjects will be recruited by methods not under the control of the local Tufts site (e.g., call centers, national advertisements)? 

No

# **C.5.3 Projected Enrollment Numbers**

We will enroll up to 60 participants, to reach our target of 30 completers (15 men and 15 women)

,	Ethnic Categories				
	Not Hispanic or Latino		Hispanic	Total	
Racial Categories	Female	Male	Female	Male	
American Indian/Alaska Native	0	0	0	0	0
Asian	3	3	0	0	6
Native Hawaiian or Other Pacific Islander	1	1	0	0	2
Black or African American	2	2	1	1	6
White	15	14	4	3	36
More than One Race	4	4	1	1	10
Total	25	24	6	5	60

- 2. *Inclusion of individuals across the lifespan:* 
  - a. Specify how you will ensure the inclusion of individuals across the lifespan. If applicable, provide a scientific or ethical rationale for the minimum and maximum age of study participants and for limiting inclusion of any age group (e.g., children or older adults): The objective of this project is to conduct a proof-of-concept study to test the feasibility of using 3D printed mini-pills to collect and characterize the microbiota in luminal content at 2 sites of the GI tract following consumption of 2 different diets. Our focus on

- older adults relates to translational relevance, this age group presents with higher rates of chronic diseases/risk factors that may be responsive to dietary modification.
- b. Include a description of expertise of the investigative team for working with individuals of the ages included, the appropriateness of the available facilities to accommodate individuals in the included age range, and how the age distribution of participants will contribute to a meaningful analysis relative to the purpose of the study: Older adults are the focus of research projects at the HNRCA. Drs. [name] and [name], as well as the HNRCA based research team has extensive experience working with this subgroup. The accessibility features in the HNRCA building were upgraded during the past 5 years to accommodate physical limitations. Given disorders of the GI tract occur throughout the lifecycle, knowledge gained from focusing on this age group will be generalizable to a broader age range of individuals.

## 3. *Inclusion of women and minorities:*

- a. Describe the projected distribution of subjects by sex/gender, race, and ethnicity. Provide the rationale for the selection in terms of the scientific objectives and proposed study design. Describe the proposed outreach programs for recruiting sex/gender, racial, and ethnic group members. If applicable, provide a reason for limiting inclusion of any group: Sex: 50% of recruited subjects will be postmenopausal women. Race/ethnicity distribution as depicted in the table above, reflects the general population distribution of older individuals (> 50 years) living in the greater Boston area, which serves as the potential pool of volunteers for this study.
- b. Provide the rationale for the selection in terms of the scientific objectives and proposed study design. Describe the proposed outreach programs for recruiting sex/gender, racial, and ethnic group members: Consistent with our study aims, the study population will focus on individuals age (≥50 years) and BMI (≥20 and ≤35 kg/m²) cutoffs (females menopausal). Past experience has shown that our recruitment methods (targeted mailers, flyers and listing on social media sites such as the HNRCA website) are effective tools in reaching our recruiting goals by sex (50/50 split). We are not targeting any specific racial or ethnic group to meet study aims.
- 4. Inclusion of Populations affected by the Disease or Condition being studied ⋈ N/A

## C.5.4 Payment

Will subjects receive money, gifts, or any other incentive for participating in this study? This does not include reimbursement for expenses, which is considered in the next section.

#### **⊠** Yes

If **Yes**, respond to all of the following:

- 1. Describe any proposed payment or incentive for subjects. Participants will be paid \$25 for the screening visit; \$140 for the enrollment visit and subsequent study visit procedures; \$90 for food pickup/food intake checklist return; \$220 for stool collection/return; and \$100 for dietary assessments, for a total of \$575.
- 2. Payment amount: \$575 if they have their eligibility verified and complete the study.
- 3. How payment will be made. Payment will be made by check mailed to the participant at the end of each diet phase. It will take approximately 2 to 3 weeks for the participants to receive the check. The PI or designate will approve payment for each participant. Payment schedules, processing dates and payment log are stored in Protocol Manager (PM). Multiple levels of

University approval are obtained outside of PM and then checks are mailed from the University to each participant. Due to federal tax law, participants will be asked to provide a social security number in order to process payments. Participants will be requested to complete a Tufts University W-9 Form (Attachment 28) provided to the HNRCA by Tufts Support Services. If participants receive over \$600 from Tufts Medical Center or Tufts University Health Sciences in a single calendar year (either in a single study or multiple studies), they will be issued an IRS 1099 form.

4. To whom payment will be made (subject, parent [which one], legally authorized representative): Participant

## 5. Payment schedule:

- a. When payment will occur: After the completion of each of the 2 diet intervention phases.
- b. The payment schedule (amount at each time point), including details about the payment schedule and amount for subjects who withdraw or are withdrawn from the study:

  Participants will receive a total of \$575 if they have their eligibility verified and complete the study. All participants who participate in the screening visit (regardless of whether they qualify for the study) will still be paid \$25 for their time and effort. Participants who withdraw from the study will be compensated for the diet phases that they completed prior to their withdrawal. Participants who withdraw partway through a phase will not be compensated.

#### **C.5.5 Reimbursement**

Will subjects be reimbursed for their expenses, such as travel, parking, meals, or any other study related costs? 

■ No

# D. Costs to Subjects

Does the research involve any costs to subjects? **☒No** 

## E. Study Design

## **E.1. Study Timelines**

- 1. Describe the duration of an individual subject's participation in the study: The entire study period will be approximately 8 weeks, starting with the enrollment visit and including a 2-week wash out period. During that period, there will be 2 diet phases: meat entrées and plant-based meat alternative entrées. Each diet phase will be ~3 weeks, variability dependent on the post-injection mini-pill recovery in stool. All study procedures will be conducted in the MRU at the HNRCA.
- 2. Describe the duration anticipated to enroll all study subjects at the Tufts study site(s): 1.5 years
- 3. Describe the estimated date for investigators to complete this study (complete primary analyses): 3 years after receiving IRB approval.

#### E.2. Procedures

1. Summarize the research design and sequentially identify all procedures to be performed to accomplish the specific aims of the project.: Participants meeting the eligibility criteria will be randomly assigned to one of two randomization sequences (Phase I and Phase II), the meat or plant-based meat alternative entrées, or vis versa, to achieve a crossover design. There will be a 2-week washout period between the phases.

During each diet phase, participants will be provided with 2 study entrées per day and counseled by the research dietitian to consume them at two different times during the day. The length of each diet phase will be ~3 weeks (i) 2 weeks of meat or plant-based meat alternative entrées, (ii) ingestion of the mini-pills on week 2 (day 14), and week 5 (day 49) of the diet phases, and (iii) additional 2 to up to 6 days (consuming 2 entrées/day) until the mini-pills are recovered from the stool. In humans, prior work has established the adequacy of the intervention period to affect microbial communities. A prior study in humans using a similar device indicated that all devices were recovered in stool using a collection window between 6 and 48 hours. The mini-pill recovery window in our study using pigs and hounds was up to 72 hours. We plan to use the appearance of blue dye in the stool to better tailor the stool collection window for our participants.

Table 1: Summar	v of Study	Timeline and	l Procedures
Table 1. Sallilla	, or braay	I IIII CIIII C WIIC	1 1 0 C C G G I C D

Study Procedures	Diet Phase I		Wash out		Diet Phase II			Total #	
Study weeks (days)	1 (1-7)	2 (8-14)	3 (15-21)	4 (22-28)	5 (29-35)	6 (36-42)	7 (43-49)	8 (50-56)	8 (56)
Food pick up	X	X	X			X	X	X	6
Entrée check list return		X	X				X	X	4
Weight	X	X				X	X		4
Waist circumference	X	X				X	X		4
Blood pressure	X	X				X	X		4
Fasting blood samples*	X	X				X	X		4
Mini-pill ingestion		X					X		2
Stool collection/return**			XXX					XXX	up to 6
Diet 24-hr recalls	X	XX					XX		5
Payment			X					X	2

\*Blood will be drawn in the morning after an overnight fast (8 to 10 hours, no food or drink except water and approved medications). The amount drawn on days 1, 14, 36 and 49 will be 12 mL (about 1 tablespoon) for a total of 48 mL over the entire study (about 4 tablespoons).

#### Diet Phase 1

Week 1\_Day 1: Following the screening visit, participants will come to the HNRCA after an 8 to 10 hour fast to return their stool sample. They will then be given the opportunity to review and sign the Study Informed Consent form and also be given the option to review and sign the Optional Tissue Banking Informed Consent form. Once enrolled, participants will have their weight, waist circumference, and blood pressure measured and provide a fasting blood sample. They will meet with a registered dietician to review instructions for entrée storage/consumption and pick up diet phase I specific entrées and checklist.

Week 2\_ Day 8: Participants will come to the HNRCA to pick up another week of study entrées and also return and review their Entrée Checklist with a registered dietician.

*Week 2-Day 14:* Participants will come to the HNRCA after an 8 to 10 hour fast to provide a fasting blood draw. They will be given a breakfast containing a study entrée specific to the diet phase to be consumed within 30 minutes, and then asked to swallow 6 mini-pills along with blue dye dispersed in ½

\*\*The number of stool samples to be collected will vary depending on mini-pill recovery

cup of water within 15 minutes. Additional water may be consumed, if desired. Participants will be given study entrées for another week and stool collection kits with cooler and instructions.

*Week 3-Days 15 to 21:* Participants will continue to consume 2 entrées per day until the mini-pills are eliminated in the stool, which can vary between 2 and 4 days, but can be up to 6 days. Participants will be asked to collect and return all stool samples produced every 48 hours, until they are informed by study staff that all pills have been recovered.

Participants can stop consuming the entrées once all mini-pills are recovered. There will be a 2 week break at this point during which participants will have no study obligations and can consume their normal diet. If all of the mini-pills are not recovered after 6 days, participants can stop consuming the study entrees, and we will conduct a 2-week follow up telephone call to inquire about symptoms or concerns.

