#### Exploratory aim:

To compare the effects of diets containing meat and plant-based meat alternatives on metabolites in stool and blood biomarkers associated with cardiometabolic risk.

The ingestible mini-pill is a non-invasive, single-use, passive collection device that is not intended for diagnosis or treatment. The mini-pills have already been developed, tested and validated by two Tufts researchers, Drs. [name] (School of Engineering) and [name] (School of Veterinary Medicine), *in vitro*, *ex vitro*, and *in vivo* in animal models (*Supplement 1: Research Strategy and Supplement 2: Soft Autonomous Ingestible Device for Sampling the Small Intestinal Microbiome, Del-Rio-Ruiz R et al.*, *manuscript in review*). A NSR device designation is being sought from the IRB to conduct a 2-phase randomized-controlled double blind crossover trial in humans by providing two entrées per day containing either meat or plant-based meat alternatives for up to 3 weeks each. After 2 weeks on each diet, participants will consume a provided breakfast meal and then be asked to swallow 6 mini-pills along with a blue food coloring dissolved in 50 mL of water, return home and collect stool samples until all the mini-pills are recovered (varies between 2 and 4 days, but can be up to 6 days). This protocol will allow us to describe the diet-induced progressive change in the GI tract microbiota prior to and including that in the stool.

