#### **Diet Phase II**

Week 6\_Day 36: Participants will come to the HNRCA after an 8 to 10 hour fast to provide a fasting blood sample and have their weight, waist circumference, and blood pressure measured. They will pick up diet phase II specific entrées and checklist.

Week 7\_ Day 43: Participants will come to the HNRCA to pick up another week of study entrées and also return and review their Entrée Checklist with a registered dietician.

Week 7-Day 49: Participants will come to the HNRCA after an 8 to 10 hour fast to provide a fasting blood draw. They will be given a breakfast containing a study entrée specific to the diet phase to be consumed within 30 minutes and then asked to swallow 6 mini-pills along with blue dye dispersed in ½ cup of water within 15 minutes. Additional water may be consumed, if desired. Participants will be given study entrées for another week and stool collection kits with cooler and instructions.

Week 8-Days 50 to 56: Participants will continue to consume 2 entrées per day until the mini-pills are eliminated in the stool, which can vary between 2 and 4 days, but can be up to 6 days. Participants will be asked to collect and return all stool samples produced every 48 hours, until they are informed by study staff that all pills have been recovered. Participants can stop consuming the entrées once all minipills are recovered. If all of the mini-pills are not recovered after 6 days, participants can stop consuming the study entrees, and we will conduct a 2-week follow up telephone call to inquire about symptoms or concerns.

Additional Study Procedures: Participants will complete one 24-hour dietary recall at the beginning of the first diet phase (baseline) and then two at the end of each diet phase over the phone. On day 1, a member of the HNRCA Dietary Assessment Unit will provide instructions and give participants a two-dimensional measuring aid (Food Amounts Booklet) to assist with estimating portion size. The first dietary recall will be completed by phone within 24 hours. Thereafter, they will be contacted by phone to complete additional 24-hour dietary recalls.

a. Procedures, situations, or materials that may be hazardous, and the precautions to be exercised to maintain subject safety: N/A.

Please also describe the following concerning procedures:

[figure not shown]

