a. How individuals will be screened for eligibility. Specify screening that will take place prior to informed consent and screening that will take place after informed consent: IRB approved telephone prescreening questionnaire will be used to determine eligibility based on inclusion and exclusion criteria (see sections C.1 and C.2). Participants who meet prescreening criteria will be invited to the HNRCA for a screening visit to confirm eligibility. At the screening visit,

after obtaining consent, BMI will be confirmed by direct measurement of height and weight. In addition, blood pressure will be measured, and medical history/medication use and dietary habits will be reviewed.

- b. *Procedures being performed to monitor subjects for safety or to minimize risks:* Every effort will be made to minimize discomfort to study subjects, with experienced nursing staff performing the blood draws and monitoring mini-pill ingestion. Post ingestion of the minipills, all participants will receive a 2 week follow up telephone call. During this call, we will review medical history in order to monitor any possible longer-term side effects including urgent/emergency visits, or hospitalizations specifically for abdominal pain/discomfort, GI obstruction, perforation, diverticulitis, GI bleeding.
  - c. All drugs and devices used in the research, their regulatory approval status (whether they are approved by the FDA and being used within their FDA approved indication), and the purpose of their use. For drugs, specify the dosage of each drug, how they will be administered, and how often they will be administered. For devices, specify how they will be used/implanted:

The mini-pill is a size 2 pill. It is not a wearable. It is not an implant. The mini-pill does not deliver any drugs. It is not intended for diagnosis or treatment. It is a passive, single-use, ingestible collection device that is recovered from the stool and its contents will be analyzed for microbial communities inhabiting the GI lumen. See Supplement 3 (Ingestible Mini-pill for Collection of GI Tract Luminal Content) which provides a detailed description, images, dimensions, designs and the safety profile of the device from both materials and our recent animal studies in hounds. An image of the pill is shown below.

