## F.6. Provisions to Monitor the Study to Ensure the Safety of Subjects

- 1. Describe the plan to periodically evaluate the data regarding both harms and benefits to assess subject safety as follows:
  - a. The data that will be reviewed, including safety data, untoward events, and efficacy data: The study subject will be monitored for discomfort during the study visit and will be accompanied at all times by a research team member. There are no medically anticipated immediate adverse effects associated with the assessments (height, weight, waist circumference, blood pressure) taken at the study visit, with consumption of the food items, or oral ingestion of the mini-pills.

Who will review the data: The study doctor will evaluate any GI or other issues reported by participants. An independent physician, [name]. Professor of Medicine and Nutrition, Tufts Medical Center/Tufts University will act as Safety Monitor and will review AEs and SAEs, if they occur and sign off on annual safety reports to the NIH.

- b. How the safety information will be obtained and documented (e.g., case report forms, by telephone calls with participants, printouts of laboratory results, etc.): Any instances of GI discomfort/side effects self-reported by participants to MRU staff via phone or at an inperson visit will be documented in REDCap.
- c. The frequency of data collection, including when safety data collection starts: If nursing staff determine a report is an AE or has potential of being an AE, the study doctor will review and the PI or designee will be sent a summary of the complaint/issue by email on the day the report has been made to the IRB and Safety Monitor.
- d. *The frequency or periodicity of review of cumulative data*: Yearly.
- e. The statistical tests for analyzing the safety data to determine whether harm is occurring: N/A
- f. Any conditions that trigger an immediate suspension of the research or other action for the research: N/A

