#### K.2. Resources Available

1. Describe the roles/tasks of each research team member here (or alternatively, you may submit any current Delegation of Authority Log you may have which already has this information completed):

Oversees research activities: [name], [name] and [name] (study-coordinator)

Reviews subject eligibility, signs subjects into study, Study MD, [name]

Performs prescreening, eligibility determination: and arranges study visits: HNRCA MRU staff

Performs assessments (height, weight, waist circumference, blood pressure diet history) and supervises ingestion of mini-pills: HNRCA MRU nursing and dietary staff

Processes blood samples and makes aliquots: HNRCA Nutrition Evaluation laboratory (NEL) staff

Performs cardiovascular disease biomarker analysis: HNRCA NEL staff

Performs GI luminal content and stool microbiome analysis: [name]

Oversees/Performs metabolome analysis: [name]

- 2. Describe the qualifications (e.g., training, experience) of the PI and research team to perform their roles. Provide enough information for the IRB to determine the PI and research team are qualified to conduct the proposed research: or ⊠ current CVs for the research team members have been submitted.
- 3. Describe the coverage plan to address any issues (including subject safety issues) that occur while the PI is away and/or unavailable. The research team member designated to serve as the acting PI in the PI's absence should have similar training and expertise as the PI: [name], a Co-I is the designated team member to serve as acting PI. She is experienced and has similar training.
- 4. Describe the process to ensure the research team members have adequate oversight and are adequately trained regarding the protocol, study procedures, and their roles and responsibilities: PI will meet with the research team weekly to review enrollment, visits, data and any study related concerns.
- 5. Medical or psychological resources that subjects might need, such as for emergencies or medical issues, are available for the study:  $\square Yes \square N/A$

T/ 3	TA /	· ·	O.1	$\mathbf{r}$		
K 1	VIII	ITI.	SITE	к	lesearc	n

K.3. Muh-She Kescaren
Is this a multi-site or collaborative study where one or more of the following is true?
☐ Tufts IRB is requested to be the Single IRB of record for non-Tufts sites or collaborators,
☐ Tufts is the sponsor,
☐ Tufts is the primary grant recipient,

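### The second mini-pill ingestion on Day 49 does not depend on recovery of the first six, and missing pills alone trigger no physician review

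*Protocol*

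**What the plan says.** Protocol E.2 (Diet Phase 1, Week 3) has participants "collect and return all stool samples produced every 48 hours, until they are informed by study staff that all pills have been recovered". It then covers the failure case, which it introduces with the words "If all of the mini-pills are not recovered after 6 days". The response it sets for that case is that "participants can stop consuming the study entrees, and we will conduct a 2-week follow up telephone call to inquire about symptoms or concerns". The safety item later in E.2 gives a 2-week call to everyone, whether or not pills are missing, and describes its content: "During this call, we will review medical history in order to monitor any possible longer-term side effects including urgent/emergency visits", with hospitalisations for named GI events also covered.

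E.2 (Diet Phase II) sets out visits on Days 36, 43 and 49. On Day 49 participants are given a study breakfast and "then asked to swallow 6 mini-pills along with blue dye". No sentence makes this depend on what was recovered in Phase I. F.1 item 3 adds a check at the start of Phase II, but only of willingness to continue.

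On oversight, F.6 states: "The study doctor will evaluate any GI or other issues reported by participants". The same section answers N/A to conditions that would trigger suspension or other action. K.2 item 4 adds: "PI will meet with the research team weekly to review enrollment, visits, data and any study related concerns".

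**The concern.** The protocol names recovery of all 12 pills as its safety endpoint (H.1 item 2), describes this as the first human use of the device (B.2 item 4) and lists obstruction and perforation among its rare risks (B.3). The endpoint is observed participant by participant before the second exposure, yet no action follows from it. A participant with pills outstanding gets essentially the same follow-up call as one with none. If that participant reports no symptoms, nothing in the text requires anyone to decide whether six more devices should be swallowed.

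B.3 already provides a study-doctor referral route for suspected aspiration. There is no counterpart for suspected retention.

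**Working it through.** The protocol states no figure to reproduce. The check is a reading of every provision that could act as a hold, plus day counts on the nominal schedule.

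**Timing (Table 1 and visit text in E.2)**

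- Interval between ingestions: 49 − 14 = 35 days.
- End of the 6-day window: 14 + 6 = Day 20.
- Call, if counted from ingestion: 14 + 14 = Day 28. That is 36 − 28 = 8 days before the Day 36 visit and 49 − 28 = 21 days before the second ingestion.
- Call, if counted from the end of the window: 14 + 6 + 14 = Day 34. That is 36 − 34 = 2 days before Day 36 and 49 − 34 = 15 days before Day 49.

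On either count the call is complete by Day 36, but its result is not linked to Day 49.

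**How unusual a pill missing at 6 days is.** Six days is 144 hours. E.2 item 1 cites full recovery of a similar human device with a 6 to 48 hour collection window, and recovery of up to 72 hours in the animal work. So 144/48 = 3 times the upper end of the cited human window and 144/72 = 2 times the animal one.

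**Stool collection after day 6: two readings**

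- *Collection stops.* B.1 has participants "collect stool samples until all the mini-pills are recovered (varies between 2 and 4 days, but can be up to 6 days", and Table 1 shows three returns per phase. Three returns at 48 hours cover 6 days, and 2 × 3 gives the table's total of up to 6. Collection then ends on Day 20, leaving 49 − 20 = 29 of the 35 days without it.
- *Collection continues.* The Week 3 text in E.2 runs it until staff report full recovery. There are then 0 days without collection, but no stated end.

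Neither reading ties the second ingestion to the count.

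**Provisions that might act as a hold**

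| Provision | What it does | Decision required for a symptom-free participant with missing pills? |
|---|---|---|
| 2-week call (E.2) | Asks about symptoms, medical history and GI-related care | No |
| Study doctor (F.6) | Evaluates reported issues | No |
| Safety Monitor (F.6) | Reviews AEs and SAEs | No |
| Weekly meeting (K.2); 35/7 = 5 between ingestions | General review | No |
| Study-doctor or PI judgment (C.2 item 17) | Excludes for a clinical condition posing a risk | No |
| Withdrawal grounds (C.4) | Include change in medical status; non-recovery not listed | No |
| Phase II check-in (F.1 item 3) | Confirms willingness | No |
| Numbered pills, accountable team member, device records (J, G.2) | Make a count possible | No |

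**Numbers exposed.** No human non-recovery rate for this device is given and none is assumed here. The group at issue is everyone who swallows Phase I pills and reaches Day 49: about the 30 target completers. The 60 enrolled is a loose ceiling, since H.2 counts everyone who signs a screening consent.

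**The case against.** The strongest reply is that silence is being read as a rule. The Diet Phase II text describes the standard schedule and does not say that participants with missing pills proceed. In the Week 3 text the 2-week break follows the sentence about full recovery, and E.1 lets phase length vary with recovery, so progress to Phase II might be taken to presuppose recovery. That reading does not hold up. The next sentence deals expressly with non-recovered participants and neither holds them back nor sends them to a decision.

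A second reply is that non-recovery is addressed. The call screens for obstruction, perforation, bleeding and abdominal pain at least 15 days before Day 49. Staff must know the count in order to tell participants when collection is complete, and nurses can escalate a report that may be an adverse event. All true, but the call and the escalation depend on something being reported, and knowing the count does not oblige anyone to act on it.

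Several points do stand:

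- Whether symptom-based follow-up is enough for a small passive capsule is a clinical judgment.
- The prior risk is reduced. Gastroparesis, chronic constipation and past obstruction are excluded (C.2), a stool sample is required within 48 hours of screening (C.3), and a similar, larger device was fully retrieved without adverse events (B.3).
- A missing pill may simply have passed unseen, and staff might well discuss it in practice.
- A hold has a design cost in a crossover.

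These limit the size of the concern. They do not supply the missing step.

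**Conclusion.** The concern holds. Followed as written, the protocol would give a participant with unrecovered Phase I pills six more on Day 49, with no required review unless symptoms or another issue had been reported. It should be fixed before participants reach Phase II. The number affected cannot be estimated from the documents and may be zero, and no harm is predicted. The conclusion rests on the text of the protocol and its nominal calendar. The supplements are not available, and the protocol does not point to them for handling missing pills. This is a participant-level safety procedure that the protocol itself sets, so it would not normally be left to a statistical analysis plan.

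**What to change.** In E.2, state that the numbered Phase I pills are reconciled by the existing Day 36 visit, before Phase II entrées are handed out. If any pill is unaccounted for, the Day 49 ingestion does not go ahead until the study doctor has reviewed the count and the follow-up call and documented a decision to proceed, delay or withhold. C.4 can cross-refer to this rule. In the same place, say whether stool collection continues past day 6 for these participants and when it ends. The clinical content of the decision belongs to the sponsor, study doctor and Safety Monitor.

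The cost is one form field and, only when a pill is missing, one documented decision at a visit that already exists. A few participants may be delayed or may not complete Phase II, which lengthens their washout or selects slightly against slow transit. The report should therefore give the numbers delayed and withheld. If the call falls on Day 34, only 2 days remain before Day 36. A decision made after Phase II entrées have started would lengthen that phase's diet exposure instead of the washout, so it is better made by Day 36.
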